## Abstract

Despite advances in pediatric sepsis care, children who develop sepsis-induced multiple organ dysfunction syndrome (MODS) face mortality rates as high as 20-50%. Multiple pathophysiological phenotypes exist in this population, with severe innate immune suppression being among the most common. Impairment of innate immune function is characterized by a reduced capacity of whole blood to produce the pro-inflammatory cytokine tumor necrosis factor ( $\text{TNF}\alpha$ ) upon ex vivo stimulation with bacterial lipopolysaccharide (LPS). When this reduction is severe ( $\text{TNF}\alpha$  response  $< 200$  pg/ml) it is termed immunoparalysis. Immunoparalysis is associated with high risks for nosocomial infection, prolonged organ dysfunction, and death. CPCCRN has developed the capacity to perform highly standardized, generalizable, functional immune monitoring that is suitable for multi-center studies including interventional trials of subject-specific immunomodulation. Our pediatric preliminary data, along with several small adult studies, suggest that granulocyte-macrophage colony-stimulating factor (GM-CSF) can reverse immunoparalysis with the potential for improving clinical outcomes. GM-CSF is FDA-approved and has a low side-effect profile, but its role in the treatment of children with sepsis-induced MODS is unclear. While a dose of  $125 \text{ mcg/m}^2/\text{day}$  for 7 days appears to be associated with reversal of immunoparalysis in small single-center studies, the optimal route of delivery (intravenous vs subcutaneous) is unknown. Further, the impact of reversal of

immunoparalysis on clinical outcomes has never been tested in the setting of a large randomized controlled trial (RCT) in children with sepsis-induced MODS.

This study represents a necessary step in the development of a multi-center placebo-controlled, double-blind RCT of GM-CSF for the reversal of immunoparalysis in this population. In GRACE we will perform an open-label multi-center interventional trial to identify an adequate dose of GM-CSF in two different routes of delivery in children with sepsis-induced MODS, with reversal of immunoparalysis as the primary outcome variable. This will include the collection and analysis of unique pharmacokinetic data that will further inform future GM-CSF dosing strategies. We will also gather feasibility and effect magnitude and variation data that will be crucial for developing a future RCT to evaluate whether GM-CSF treatment reduces sepsis-induced MODS.

## 1 Study Summary

This study is an open-label, multi-center, interventional trial in which children with sepsis-induced MODS undergo surveillance immune function testing beginning on Day 2 of MODS. Those children who demonstrate immunoparalysis ( $\text{TNF}\alpha$  response  $< 200$  pg/ml) will receive a 7-day course of GM-CSF at a dose of  $125$  or  $250$  mcg/m^2/day by either the intravenous (IV) or subcutaneous (SQ) route.

The goal of the study is to establish the dose and route of delivery that results in resolution of immunoparalysis ( $\text{TNF}\alpha$  response  $\geq 200$  pg/ml) by the morning after the 3rd scheduled dose with persistent resolution of immunoparalysis on the morning after the 7th scheduled dose. Resolution of immunoparalysis in 8 out of the first 10 subjects in a study treatment arm represents a successful dose and route. The goal of this study will be achieved through the following Specific Aims:

**Specific Aim 1.** Establish the immunologic efficacy of GM-CSF administered by the IV and SQ routes in children with immunoparalysis in the setting of sepsis-induced MODS.

**Specific Aim 2.** Estimate the pharmacokinetic parameters by the IV and SQ GM-CSF administered in pediatric sepsis-induced MODS.

**Specific Aim 3.** Demonstrate the feasibility of screening, enrollment, drug delivery, and sample collection for a multi-center immunostimulation trial in children with sepsis-induced MODS.

## 2 Rationale and Background

### 2.1 Sepsis, MODS, and innate immune suppression

Severe sepsis/septic shock remain a major source of pediatric morbidity and mortality worldwide, with the highest rates of adverse outcomes seen in children who develop failure of two or more organs. Children with sepsis-induced multiple organ dysfunction syndrome (MODS) represent a heterogeneous group of patients who have been shown to have several distinct phenotypes of underlying pathophysiology [1]. One common phenotype is that related to an exaggerated compensatory anti-inflammatory response. Impairment of the innate immune system is common and measurable in pediatric sepsis. Innate immune cells such as monocytes and neutrophils serve critical functions including migration to sites of infection, phagocytosis of pathogens, promotion of microbial killing, antigen presentation, and production of immunomodulatory cytokines. *Reductions* in pro-inflammatory cytokine production capacity have been shown to occur commonly following the onset of sepsis in adults [2, 3, 4, 5, 6], often carrying associations with nosocomial infection and death. We have shown similar associations between innate immune suppression and adverse outcomes in children with multiple organ dysfunction syndrome and sepsis. [7, 8]

### 2.2 Whole Blood *ex vivo* LPS-induced TNF $\alpha$ production capacity

Stimulation of whole blood with lipopolysaccharide (LPS) allows for quantification of the innate immune systems responsiveness to a challenge. LPS stimulation should result in rapid and robust production of the proinflammatory cytokine tumor necrosis factor (TNF $\alpha$ ). Severe reductions in the TNF $\alpha$  response have been associated with increased risks for infection and death [7, 8, 9, 10, 11, 12]. To assure consistency between investigators, CPCCRN uses a consistent LPS type with rigorous quality control procedures, small blood volumes appropriate for pediatric studies, a four-hour incubation period (suitable for same-day testing), and TNF $\alpha$  quantitation on a highly automated, Good Laboratory Practices instrument. The *Immulin* 1000 (Siemens, Deerfield, IL) is an automated chemiluminometer that is used to measure hormones and other analytes in clinical laboratory studies. We use this instrument to perform cytokine measurements, under a Research Use Agreement, using commercially available test units that are used clinically in Europe for patient management. The intra-assay coefficient of variation for the TNF $\alpha$  assay on the *Immulin* is less than 10%. By using the *Immulin* we avoid the need to perform highly operator-dependent assays such as enzyme-linked immunosorbent assays

(ELISAs).

## 2.3 Reversibility of innate immune suppression through GM-CSF therapy

GM-CSF is an endogenous, immunostimulating cytokine produced primarily by TH1 lymphocytes. It is available in recombinant human form (sargramostim, Leukine; Bayer Healthcare Pharmaceuticals, Montville, NJ) and has been FDA-approved for bone marrow reconstitution following bone marrow transplantation (BMT) since 1991. It has a long track record of safe use in acutely and critically ill patients, including children, with a low incidence of adverse events[13, 14, 15]. Rapid IV administration of GM-CSF (over  $\leq 2$  hours) has been associated with respiratory distress, peripheral edema (11% incidence with GM-CSF vs 7% incidence with placebo) and pericardial effusion (4% vs 1%), but this appears to be related to the rate of infusion[16]. These side effects have not been associated with infusion durations of  $> 2$  hours or via the SQ route.

Monocyte hyporesponsiveness has been shown to be reversible *in vitro* through co-culture with GM-CSF [17, 18, 19, 20, 21]. GM-CSF has been used in four small published immunomodulation studies in critically ill adults, summarized in Table 1 on the facing page. The doses used were substantially lower than the FDA-approved used for bone marrow reconstitution (250 g/m^2/day). In all four adult studies, immune recovery was prompt (within 3 days of initiation of GM-CSF therapy) though it is unclear if longer durations of therapy were necessary to prevent relapse of innate immune depression. There were no serious adverse events ascribed to GM-CSF in any of the studies. GM-CSF therapy did not result in increased systemic inflammation as measured by plasma levels of the pro-inflammatory cytokines interleukin (IL)-6 or IL-8.

## 2.4 Immunoparalysis and MAS

Sepsis induced multiple organ dysfunction syndrome (MODS) is a poorly understood syndrome for which treatment is directed by organ failure instead of inflammation biomarker responses. CPCCRN investigators [1] have identified several distinct sepsis phenotypes. Another phenotype of pediatric sepsis-induced MODS is one analogous to macrophage activation syndrome (MAS), characterized by high serum ferritin levels ( $\geq 2,000$  ng/ml). The MAS phenotype is relatively uncommon ( $<10\%$  of sepsis-induced MODS that we have studied), but represents a potential contraindication to receipt of GM-CSF therapy. We will therefore screen for and exclude children with serum ferritin levels  $\geq 2,000$  ng/ml.

Author, Year, [Ref]	Patient Population	Trial Design	GM-CSF Regimen	Patients Dosed with GM-CSF	Result
Presneill et al, 2002 [23]	Septic adults	Placebo-controlled RCT	3 g/kg/day (~90g/m  /day) IV x 5 days	10	Increased neutrophil function and oxygenation
Nierhaus et al, 2003 [24]	Septic adults	Uncontrolled case series	5 g/kg/day (~200g/m  /day) SQ x 3 days	9	Increased monocyte HLA-DR expression, TNF production capacity, and 66% survival
Rosenbloom et al, 2005 [25]	Septic adults	Placebo controlled RCT	125 g/m  (~4g/kg) IV over 3 days	18	Increased monocyte HLA-DR expression, faster resolution of infection
Meisel et al, 2009 [26]	Septic adults	Placebo controlled RCT	4 g/kg/day (~125 g/m  /day) SQ x 8 days	19	Increased monocyte HLA-DR expression, TNF production capacity, improved illness severity

ALI: acute lung injury, RCT: randomized, controlled trial, SQ: subcutaneous.

Table 1: Clinical Evidence for the Use of GM-CSF for Immunomodulation in Critically Ill Adults

## 3 Subject Eligibility, Accrual and Study Duration

### 3.1 Eligibility criteria

Inclusion criteria are:

- $\geq 40$  weeks gestational age to  $< 18$  years; AND
- Onset of  $\geq 2$  new organ dysfunctions (compared to pre-sepsis baseline) as measured by the Proulx criteria; AND
- Documented or suspected infection as the MODS inciting event.

Exclusion criteria are:

- Weight  $< 5\text{kg}$ ; OR
- Limitation of care order at the time of screening; OR
- Patients at high risk for brain death; OR
- Active (or planned within 7 days) immunosuppressive treatment; OR
- Known primary immunodeficiency disorder; OR
- Diagnosis of myeloid leukemia, myelodysplasia, or autoimmune thrombocytopenia; OR
- Known allergy to GM-CSF; OR
- Documented hyperferritinemia (serum ferritin  $\geq 2,000$  ng/ml) during current sepsis event; OR
- Contraindication to SQ injection (ECMO); OR
- Burns where  $> 5\%$  of the total body surface area is affected; OR
- Renal replacement therapy at the time of screening; OR
- On ECMO or anticipated to require ECMO; OR
- Known pregnancy; OR
- Inability to collect and ship sample for immune testing on MODS Day 2; OR
- Previous enrollment in the GRACE study.

These criteria were chosen in order to identify children with early, sepsis-induced MODS and to exclude children for whom GM-CSF is unlikely to be beneficial (children with limitation of care orders), those for whom the effect of GM-CSF may be altered by the receipt of active immunosuppression, those with known contraindications to GM-CSF, and those with concurrent secondary hemophagocytic lymphohistiocytosis (HLH) or macrophage activation syndrome (MAS).

### 3.2 Subject Accrual and Study Duration

This study will require 20 to 30 evaluable subjects. We define an evaluable subject as a subject who receives all 7 doses of GM-CSF (with an exception made when WBC > 50K cells/mm^3), and from whom both Drug Day 4 and Drug Day 8 immune testing samples were obtained. We anticipate that approximately one third of enrolled subjects will qualify to receive GM-CSF, and anticipate that half of the subjects receiving GM-CSF will be evaluable due to post-enrollment exclusions described below. This will require enrollment of up to 180 subjects.

The CPCCRN network enrolled over 400 subjects with multiple organ failure in two years in a previous study. We estimate that each of the eight participating hospitals will have 8 to 10 eligible patients per year. Study completion will require up to three years of subject accrual.

## 4 Study Design and Procedures

Sepsis-induced MODS remains an important source of morbidity and mortality in the PICU. We have demonstrated that failure of the immune system is a common feature of this disease state and is associated with high risks for the development of prolonged organ failure, nosocomial infection, and death. Using our small blood-volume immune function monitoring approach, our preliminary data suggest that immunoparalysis is reversible with the potential for improved clinical outcomes in this setting. The study is a prospective project designed to measure the effect of treatment with GM-CSF on innate immune function when given by the IV or SQ routes in children with demonstrated immunoparalysis in the setting of sepsis-induced MODS. The study workflow is summarized in [Figure 1 on the next page](#).

### 4.1 Screening and Enrollment

All patients admitted to the pediatric or cardiac ICU at CPCCRN sites will be evaluated for study eligibility.

Patients who meet inclusion criteria will be entered into the data capture system and exclusion criteria will be recorded in that system. If the patient is eligible (no exclusion criteria are present) then the legal guardian(s) will be approached and offered the opportunity for their child to participate in the GRACE study. We will perform immune function screening beginning on Day 2 of sepsis-induced MODS (MODS Day 2).

[figure not shown]

Figure 1: Diagram of the GRACE Study Workflow

## 4.2 Assessment of Innate Immune Function

Once a subject is enrolled on the GRACE study, the subject will undergo a 1.5 ml blood draw for measurement of whole blood LPS-induced  $\text{TNF}\alpha$  production capacity ( $\text{TNF}\alpha$  response), serum ferritin, plasma IL-6 and IL-8 levels. Enrolled subjects who demonstrate severe leukopenia ( $\text{WBC} < 2\text{K}$ ) at the time of planned screening sampling will not undergo sampling on that day, but will be re-sampled at the time of the next planned screening day provided their WBC count has increased to  $\geq 2\text{K}$ . Blood samples will be stimulated on-site within one hour of sample collection using highly standardized LPS stimulation kits provided by the Immune Surveillance Laboratory (ISL) at the Research Institute at Nationwide Children's Hospital. Aliquots of  $50\ \mu\text{L}$  of whole blood will be stimulated in duplicate with LPS as well as two controls, consuming approximately  $200\ \mu\text{L}$ . The LPS incubation period is four hours. Samples are immediately centrifuged and all supernatants will be overnight-shipped on dry ice to the ISL where  $\text{TNF}\alpha$  production capacity and serum ferritin levels will be measured the next morning (MODS Day 3). If a subject's  $\text{TNF}\alpha$  production capacity is  $< 200\ \text{pg/ml}$  and the serum ferritin is  $< 2,000\ \text{ng/ml}$ , the subject has documented immunoparalysis without MAS, and is eligible to be considered for GM-CSF administration. If immune function is normal, but MODS remains present, the subject will have repeat testing twice a week until resolution of MODS, MODS duration  $> 20$  days, discharge from the ICU, or death. Repeat testing would be on days  $6 \pm 1$ ,  $9 \pm 1$ ,  $13 \pm 1$ ,  $16 \pm 1$ , and  $20 \pm 1$ . If test results indicate that the subject has

documented immunoparalysis without MAS, the subject is eligible to be considered for GM-CSF administration. Subjects who have improved to single-organ dysfunction on the first day of GM-CSF administration will also undergo measurement of their  $\text{TNF}\alpha$  production capacity prior to receiving their first dose of GM-CSF, but these samples will not be analyzed in real-time. Rather, they will be batch-shipped with the later immune function samples.

Subjects who receive GM-CSF will undergo repeat innate immune function and ferritin testing the morning after their 3rd and 7th scheduled doses of GM-CSF to monitor the effect of GM-CSF on immunoparalysis associated with pediatric sepsis-induced MODS, as well as to reassess serum ferritin. Immune function testing is summarized in Figure 2.

[figure not shown]

Figure 2: Schematic of the GRACE Study

If the serum ferritin is  $\geq 2,000$  ng/ml, the subject ends further study participation permanently, and the site will be immediately notified so that site-specific confirmation and management of hyperferritinemia can take place.

The Nationwide Children's site is able to assess subject eligibility on the same day as LPS stimulation (MODS Day 2), but GM-CSF administration will be delayed until the next morning (MODS Day 3) in order to remain consistent with the dosing schedule at other CPCCRN sites.

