### 4.3 Eligibility to Receive Initial GM-CSF Dose

Subjects eligible to be considered for initial administration of GM-CSF will receive study drug if the following additional requirements are met:

- No diagnosis of pregnancy.
- The presence of dysfunction of at least one organ system
- Subject remains in ICU.
- WBC  $\leq 50K$  cells/mm^3.
- CRRT is not being used and there are no immediate plans to start.
- No new immunosuppressive drugs are being given or planned in the next 7 days.
- Not on ECMO or have immediate plans to start ECMO.

The WBC measurement is required prior to GM-CSF, and must be the most recent measurement prior to drug administration. The sample must be no earlier than 6 hours prior to drug administration.

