## 4.5 Assignment of Treatment Arms

Study drug will be administered in 4 sequential treatment arms (125 mcg/m^2/day IV, 250 mcg/m^2/day IV, 125 mcg/m^2/day SQ, 250 mcg/m^2/day SQ) dependent on the success of an arm. Enrollment will begin in the 125 mcg IV arm. If 125 mcg IV does not prove successful, we will move to the 250 mcg IV dose arm. If an IV arm is successful, we will open a SQ arm at the same treatment dose level that the IV arm completed. If we begin with 125 mcg SQ arm, then we will move to the 250 SQ arm if the 125 SQ arm is not successful.

A subject is considered to have failed to achieve resolution of immunoparalysis if the  $\text{TNF}\alpha$  response is  $< 200$  pg/ml on Drug Days 4 or 8. If a 3rd subject in a 125 mcg dose arm fails to respond to study drug, that arm is considered to have failed, and no further subjects will be enrolled in that arm. Enrollment will proceed to the 250 mcg arm for the respective route (IV or SC). In the 250 mcg arms, we will enroll fully to ten evaluable subjects even if these arms have 3 or more subjects who do not respond. This is to fully understand the PK of the drug at this FDA approved dose.

A successful dose and route is defined as the resolution of immunoparalysis in 8 out of the first 10 subjects in a treatment arm. Enrollment will not stop early in a study treatment arm due to achieving 8 successes. Instead we will continue to enroll until that study treatment arm is complete and we have confirmed that the arm has a sufficient number (ten) of evaluable subjects who have received study drug.

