### 5 GM-CSF Administration

#### 5.1 IV Infusion Arms

The first dose of the study drug will be infused over a minimum of 6 hours on the day after the qualifying immune testing sample. The infusion may be interrupted if needed, but must run over a total of no more than 12 hours. GM-CSF may be given via a peripheral or central IV catheter. The first administered dose of GM-CSF will be initiated within 4 hours after receipt of notification of qualification for drug. If the 4 hours elapse, GM-CSF

	Schedule of Events	Drug Study Day										9-21/ hospital discharge	22 - hospital discharge
		1	2	3	4	5	6	7	8				
	GM-CSF administration	X	X	X	X	X	X	X					
	AE monitoring	X	X	X	X	X	X	X	X		X		
	AE resolution monitoring	X	X	X	X	X	X	X	X		X		X
	PK sampling			X				X					
	1.5 mL blood sample prior to GM-CSF (4AM- noon) immune function/ferritin testing				X				X				
	Sample shipment to Nationwide Initial immune function/ferritin testing				X								
	Tracheal aspirates	X	X	X	X	X	X	X	X				
	Batch shipment to Nationwide PK samples, tracheal aspirates, and final immune function samples	X	X	X	X	X	X	X	X				

Table 2: Summary of Study Events

should still be started as soon as possible. Subjects who have initiated the study drug treatment course will need to continually qualify for subsequent doses as indicated under the protocol section 4.4 for subsequent GM-CSF doses. All subsequent IV doses will be initiated between 4 AM and noon. If the window is missed, GM-CSF should still be given as soon as possible.

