## 6 Statistical Analysis

Statistical analyses and comparisons for this study will be primarily descriptive. The cohort will be characterized with simple statistical summaries, i.e. frequencies, means, standard deviations, medians, and interquartile ranges. An arm will be considered

successful if 8 of the first 10 completing subjects in the arm have a good immune response, i.e.  $\text{TNF}\alpha > 200$  pg/mL on Drug Days 4 and 8. Figures will be created to illustrate the distribution over the treatment course of  $\text{TNF}\alpha$ , IL-6, and IL-8. Pharmacokinetic modeling of GM-CSF will be conducted using non-linear mixed models as implemented in NONMEM (version VI, ICON Development Solutions, [name]). All other inferential analyses that may be conducted will be considered exploratory and will be reported as such.

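### The pre-dose TNFα sample drawn in children improved to single-organ dysfunction has no role in the 8-of-10 rule, so recovery that preceded GM-CSF can be counted as resolution

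*Combined protocol and SAP*

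**What the plan says.** Aim 1 in section 1 is to "Establish the immunologic efficacy of GM-CSF administered by the IV and SQ routes in children with immunoparalysis". A child qualifies on a screening sample with TNFα response below 200 pg/ml and ferritin below 2,000 ng/ml (section 4.2). In the IV arms the first infusion is given "on the day after the qualifying immune testing sample" (section 5.1). By then the organ criterion is only "The presence of dysfunction of at least one organ system" (section 4.3), so a child who has improved since screening can still be treated.

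For children who have improved to single-organ dysfunction by Drug Day 1, section 4.2 adds a TNFα measurement "prior to receiving their first dose of GM-CSF, but these samples will not be analyzed in real-time". The samples travel in a batch with the later immune function samples.

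The counting rules look only at Drug Days 4 and 8:

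- Evaluable (section 3.2): all seven doses, with an exception for high WBC, and both the Day 4 and Day 8 samples.
- Subject failure (section 4.5): "A subject is considered to have failed to achieve resolution of immunoparalysis if the" TNFα response is below 200 pg/ml on Drug Day 4 or 8.
- Arm success (section 4.5): "A successful dose and route is defined as the resolution of immunoparalysis in 8 out of the first 10 subjects in a treatment arm". Section 6 has the arm "successful if 8 of the first 10 completing subjects in the arm have a good immune response", judged on Drug Days 4 and 8.
- Arm failure at the lower dose (section 4.5): "If a 3rd subject in a 125 mcg dose arm fails to respond to study drug, that arm is considered to have failed".
- Replacement (section 4.7): a list of reasons, none of which is a pre-dose value at or above 200 pg/ml.

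**The concern.** Resolution implies that the condition was present when treatment began. The rule does not check this, even for the children in whom the plan collects the measurement that would show it. A child whose TNFα response had returned above the threshold between the screening sample and dose 1, and who stays above it, adds one success to a count meant to measure the effect of GM-CSF on immunoparalysis.

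The count is the trial's only efficacy criterion, and it has no concurrent control. It also steers the trial: under section 4.5 a successful 125 mcg IV arm leads to the SQ arm at the same level, and the 250 mcg IV arm is opened only if 125 mcg IV does not succeed. The abstract says that effect magnitude and variation from this study will inform a later RCT, so an inflated proportion would be carried forward.

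**Working it through.** **The plan's own figure.** Section 3.2 needs up to 30 evaluable subjects, expects one third of those enrolled to qualify for drug, and half of those dosed to be evaluable: 30 / (1/3 × 1/2) = 180, which matches the stated maximum. The documents state no error rate, power or target response for the 8-of-10 rule, so there is none to reproduce.

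**The rule.** An arm passes if at least 8 of 10 evaluable subjects respond. Stopping a 125 mcg arm at the third failure does not alter this probability, because ten subjects with at most two failures is the same event. For response probability q:

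P(pass) = 45 q⁸(1−q)² + 10 q⁹(1−q) + q¹⁰

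At q = 0.6 this is 0.1209 + 0.0403 + 0.0060 = 0.167. At q = 0.5 it is 0.055, and at q = 0.8 it is 0.678.

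**Effect of children recovered before dose 1.** Three quantities are assumptions, because the documents give none of them:

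- f: share of counted (evaluable) subjects already at or above 200 pg/ml before dose 1
- s: chance that such a child is at or above 200 pg/ml on both Day 4 and Day 8
- p: response rate in children still immunoparalysed at dose 1

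Apparent response: q = f·s + (1−f)·p. The shift is q − p = f(s − p), so the count is inflated relative to p whenever s exceeds p.

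| p | f | q at s = 0.8 | P(pass) | q at s = 1 | P(pass) |
|---|---|---|---|---|---|
| 0.6 | 0 | 0.60 | 16.7% | 0.60 | 16.7% |
| 0.6 | 0.1 | 0.62 | 20.2% | 0.64 | 24.1% |
| 0.6 | 0.2 | 0.64 | 24.1% | 0.68 | 33.1% |
| 0.5 | 0 | 0.50 | 5.5% | 0.50 | 5.5% |
| 0.5 | 0.1 | 0.53 | 7.9% | 0.55 | 10.0% |
| 0.5 | 0.2 | 0.56 | 11.1% | 0.60 | 16.7% |

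The effect can also be small. If 20% of counted children had improved to one organ and 30% of those had recovered immune function, f = 0.06. With p = 0.6 and s = 1, q = 0.624 and P(pass) is 20.9%. At p = 0.4, f = 0.1 and s = 1, q = 0.46 and P(pass) goes from 1.2% to 3.2%. At p = 0.8 with s = 0.8 there is no shift at all.

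**What one arm's result would look like.** An observed 8/10 (80%, exact 95% CI 44% to 97%) that includes two such children is (8 − 2)/(10 − 2) = 6/8 among the rest: 75%, exact 95% CI 35% to 97%.

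**The case against.** The strongest reply is that the plan defines documented immunoparalysis by the screening result, which is what is known when treatment is decided. Counting everyone treated on that result is a coherent estimand, and removing children on a value unknown at dosing is a post-treatment exclusion. Much of this stands. It argues against forcing replacement, and for keeping the count as defined. It does not argue against showing, beside it, the count without children already above the threshold. The measurement predates treatment, so excluding on it whatever the later outcome does not condition on response.

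A second reply is that section 6 calls the analysis primarily descriptive. It does, but the same section sets the 8-of-10 criterion, and section 4.5 uses that criterion to choose the next arm.

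Several stronger readings are tempting and go beyond the documents:

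- *The plan acknowledges that these children may have recovered.* Section 4.2 orders the sample and gives no reason.
- *Every child recovered before dose 1 becomes a success.* Only those who are evaluable and at or above 200 pg/ml on both days do. Early discharge before all doses leads to replacement, which may remove some of the fastest improvers.
- *The delayed assay is the fault.* The pre-dose sample is shipped with the later immune samples, and under section 4.9 the Day 8 sample is itself batch-shipped, so both can inform the same decision.
- *The omission from Table 2 shows that the sample was forgotten.* It is conditional, and Figure 2, which summarises immune testing, and the Manual of Operations could not be checked.
- *Using the sample would remove spontaneous recovery and regression to the mean.* Recovery between dose 1 and Day 4 or 8 has a longer window than the roughly one-day gap before dosing, and still counts as success.

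**Conclusion.** The gap is real. Followed exactly, the stated rules count an evaluable child who was above the threshold before dose 1, and on both assessment days, as a GM-CSF resolution, although for single-organ children the plan holds the value that would reveal it. The direction is upward provided such children stay recovered more often than the others respond (s above p), which is plausible but not documented. The size is not established. At p = 0.6, the chance of declaring success rises from 16.7% to 20–24% for f = 10% and to 24–33% for f = 20%, with 80–100% persistence; smaller f, or s close to p, makes it minor. A reader might infer that the arm decisions are unreliable, or that these children must be replaced. The documents support neither: they give no recovery frequency, and replacement is a design preference. What is supported is that the handling of a known pre-dose value should be settled before results are seen.

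**What to change.** Add to section 6:

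1. Each arm's result is reported as defined, and again excluding every subject with a known pre-dose TNFα response at or above 200 pg/ml, whatever the outcome on Days 4 and 8. The second result is given as x/n with an exact confidence interval, since its denominator may be below ten.
2. The pre-dose results are available when the arm decision is made, so that both figures can be seen then.
3. In subjects with a pre-dose sample, change in TNFα is measured from that value.
4. The effect estimate carried to the RCT shows both figures.
5. The correction is partial: subjects with two or more organ dysfunctions at dose 1 have no pre-dose value, and spontaneous recovery after dose 1 is not addressed.

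The samples are already planned, so the cost is wording and timely assay of the batch. The downside is a slightly smaller denominator and possibly a less favourable second figure. No dosing or eligibility rule changes.

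Two further steps are optional. Replacing such subjects would raise maximum enrolment to 180/(1 − f): about 200, 225 or 257 at f = 10%, 20% or 30%. Section 3.2 implies 8 sites × 8 to 10 patients × 3 years = 192 to 240 eligible patients, so the larger values may be out of reach. Extending the pre-dose draw to every treated child would close the gap for multi-organ children. The assay consumes about 0.2 ml, but the immune samples are specified as 1.5 ml draws, and section 10.3.2 already foresees truncated sampling to stay under 3 ml/kg.
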